7.1.2 Name : Miltefosine (Impavido[®])

Class: Phosphocholine analogue.

Mechanism of action: interferes with the synthesis and metabolism of phospholipids.

It may also interfere with the parasite's membrane signal transduction, and glycosylphosphatidylinositol anchor biosynthesis.

Commercial source: Knight Therapeutics

Product appearance: comes as 10mg and 50mg capsules as a pack of 28 or 56 capsules sealed in 4 or 8 aluminium blister stripes, each containing 7 capsules.

Administration: oral, with food. For miltefosine, there are no known interactions with other commonly used medications, though this cannot be excluded.

7.2 Doses and treatment regimens

Ambisome[®] monotherapy 5 x 4 mg/kg IV at D1, D4, D8, D11 and D15.

Combination of Ambisome[®] (5 x 4 mg/kg IV at D1, D4, D8, D11 and D15) plus miltefosine orally BID administration (allometric dosing) for 3 weeks.

Table 1 below describes the miltefosine regimen by an allometric scale, to be used for patients up to 30Kg.

Patients with weight > 30Kg, there is no difference between the allometric scale and conventional dose of 2.5mg/Kg/day. For these patients, the miltefosine regimen will be:

Patients > 30Kg and < 45Kg: 100mg of miltefosine per day, administered as 1 capsule of 50mg in the morning and 1 capsule of 50mg in the afternoon, with food, for 21 days.

Patients > 45Kg: 150mg of miltefosine per day, administered as 2 capsules of 50mg in the morning and 1 capsule of 50mg in the afternoon, with food, for 21 days.

An easy-to-use table (Table 2) with dosing scheme by weight and height will be provided to the investigators to define the exact daily miltefosine dose to be administered.

FEMALE									
HT (cm)	80-89	90-99	100-109	110-119	120-129	130-139	140-149	150-159	160
WT (kg)									
7									
8	30								
9	30			RISK	DF SE	/ERE N	ΛΑΙΝΙ	JTRITI	ON
10	30	40			REFER TO	THE WHO F	REFERENCE	CURVES	
11	40	40	40					0011120	
12	40	40	40						
13	40	40	40						
14	40	40	40	50					
15	40	40	50	50					
16	40	50	50	50					
17	40	50	50	50	50				
18	50	50	50	50	60				
19	50	50	50	60	60				
20	50	50	50	60	60	60			
21	50	50	60	60	60	60			
22	50	50	60	60	60	60			
23	50	50	60	60	60	70	70		
24	50	50	60	60	60	70	70		
25	50	60	60	60	70	70	70		
26	50	60	60	60	70	70	70	70	
27	50	60	60	70	70	70	70	80	
28	50	60	60	70	70	70		80	
29	50	60	60	70	70	70	80	80	00
30	50	60	60	70	70	80	80	80	80

Table 1 Daily allometric miltefosine dose for female and male children based on fat-free mass

Protocol Version/Date: V3.0, 25 Feb 2020

MALE									
HT (cm)	80-89	90-99	100-109	110-119	120-129	130-139	140-149	150-159	160
WT (kg)									
7									
8	40								
9	40			RISK	OF SEV	/FRF N	ΛΑΙ ΝΙ	JTRITI	ON
10	40	40				THE WHO F			•••
10	40 40	40 40			KLI LK IU		ALF LIVENCE	CORVES	
11	40 40								
12	50	50	50						
13	50	50	50						
15	50	50	60	60					
16	50	50	60	60					
17	50	60	60	60					
18	50	60	60	60	70				
19	50	60	60	70	70				
20	50	60	60	70	70				
21	60	60	60	70	70	70			
22	60	60	70	70	70	80			
23	60	60	70	70	80	80			
24	60	60	70	70	80		80		
25	60	60	70	70	80		80		
26	60	70	70	80	80		100		
27	60	70	70	80	80		100		
28	60	70	70	80	80		100	100	
29	60	70	70	80	80		100		
30	60	70	80	80	100	100	100	100	

Administration of the daily dosage must be divided in 2 administrations, during or after a meal, to avoid direct gastrointestinal adverse effects of miltefosine, as follows:

Total daily dose, divided:	30mg	40mg	50mg	60mg	70mg	80mg	90mg	100mg
Morning	2x	2x	1x	1x	1x	1x	1x	1x
(breakfast)	10mg	10mg	50mg	50mg	50mg	50mg	50mg	50mg
Afternoon	1x	2x		1x	2x	3x	1x	1x
(dinner)	10mg	10mg		10mg	10mg	10mg	50mg	50mg

Table 2 Morning and afternoon doses

With this scheme, a maximum of 3 capsules of 10mg will be administered per intake.

All administrations of Ambisome[®] will be directly observed by the study nurse in the hospital to assure compliance. Subjects will be admitted for whole duration of Ambisome[®] administration. In case of combination arm of Ambisome[®] and miltefosine, miltefosine administration will be directly observed by the study nurse for the time subject is admitted in the hospital. After each drug intake all subjects will be observed for vomiting for 30 minutes. All vomiting episodes will be recorded. In case of vomiting 30 minutes after miltefosine intake, the dose will be re-administered. If a repeated vomiting occurs (vomiting after re-dose) the treatment will not be re-administered.

Patients allocated in the combination arm may be discharged on day 16 and given the remaining doses of Miltefosine to be taken at home. Each subject will be contacted by telephone by a health worker on a daily basis until completion of the Miltefosine treatment. It is also permissible for a subject to be hospitalized for the entire duration of treatment for those in the combination arm.

Compliance will be assessed by total dose taken by the patient. Full compliance will be considered if 90-110% of the prescribed dose is administered.

If the patient vomits a dose within 30min of drug intake and is re-dosed (without vomiting this 2nd re-dose), the re-dose will be considered for compliance. However, if the patient is not re-dosed within 30min or if s/he vomits the re-dose, this dose will not be accounted for compliance.

In the case of a patient vomiting after 30min of miltefosine intake, the dose will be accounted for compliance.

In the Miltefosine regimen, treatment may be temporarily interrupted (due to AEs or at the discretion of the investigator) and resumed if this interval is no longer than 72 hours. Once resumed, the subject will complete the 21 days of treatment by prolonging the treatment up to Day 24 (missing doses will be compensated). In this case, the total administered dose will still be within the 90% range of full compliance, therefore it will not be considered a compliance deviation.

If treatment needs to be interrupted for > 72 hours due to an AE, rescue treatment will be considered, at the discretion of the investigator.

7.3 Study treatments labelling, packaging

Commercially available Ambisome[®] and miltefosine will be used. Trial specific labelling will be applied prior to use.

7.4 Accountability

All study medications must be kept in a locked room that can be accessed only by the appropriate study personnel designated by the investigator. The study medications must not be used for purposes other than this protocol. Under no circumstances may the investigator or site staff supply study medications to other investigators or sites or allow the medications to be used other than as directed by this protocol without prior authorization from the sponsor or delegated responsible party.

Specific study forms for drug accountability will be designed to allow for adequate records on receipt, use, return, loss, or other disposition of medication. These accountability forms must be maintained in a locked cabinet by the study pharmacist or designated personnel. Since the

same drugs are used in routine practice, SOPs for labelling the boxes to be used in the trial will be developed, and the drugs used in the trial will be trial specifically labelled and stored completely separated from the routine drugs.

In case of Miltefosine treatment given to patient to be taken at home, the subjects will be instructed to return the empty blisters in order for site staff to perform full accountability. The compliance is assessed and reported in the CRF.

7.5 Storage

Study drug must be kept in a locked cabinet and/or in a room with restricted access, under the control of the study pharmacist.

Temperature of the storage location will be monitored daily and recorded in a temperature log. In the event of temperature excursions below or above the allowable range site staff must inform the study monitor.

Ambisome[®]: The product should be stored at 25°C or below, not frozen or exposed to light. The shelf life is 3 to 4 years. Once reconstituted, chemical and physical in-use stability has been demonstrated for 24 hours at 25+/-2°C in vials exposed to ambient light. This is increased to 7 days if stored at 2-8°C. However, to avoid contamination, once reconstituted, the product should be stored at 2-8°C and be used within 24 hours. Vials will be exclusive to each patient. Storage to these requirements will be ensured throughout the study.

Miltefosine: The product should be stored in the original package and protected from moisture at 20-25°C, with excursions permitted at 15-30°C. The shelf life is 5 years. Packaging should be undamaged prior to use.

7.6 Blinding and procedures for unblinding

Not applicable. This is an open label study.

7.7 Concomitant treatments

All medications required for concomitant conditions should be postponed until after the end of treatment for PKDL, unless warranted by immediate medical need. Common conditions such as malaria and respiratory tract infections should be treated prior to starting PKDL treatment.

There are no known interactions with other commonly used medications, though this cannot be excluded. All concomitant medications used during the study up to 24 months visit shall be recorded in the patients' chart and in the CRF.

7.8 Rescue and Escape treatments

At any time-point during the study, if the patient does not respond to treatment, or lesions are worsening, or if after the healing period, the lesions reappear/reactivate, rescue treatment can be initiated at the discretion of the study investigator. A subject who receive rescue treatment at any time during the trial will be considered a treatment failure and will be withdrawn from the study. Rescue treatment will be provided to the patient as per standard recommendations by National Program with Miltefosine monotherapy for 12 weeks.

Patients will be given rescue treatment if:

- Progression of the disease is documented at any point in time during the study treatment or FU, and rescue treatment is indicated by the investigator
- They fail to tolerate trial medication or if occurrence of adverse event(s) during receipt of test drug dose (refer to the Ambisome[®] pack insert for withdrawing the patients) requires permanent interruption of treatment, and rescue treatment is indicated by the investigator
- If after healing period lesions reappear/reactivate

8 Study Assessments

8.1 Timing of Assessments:

Study assessments will be performed at baseline, D1, D8, D15, D22 (only for subjects allocated to combination arm), and D30 (EOT, +/- 3 days) during treatment phase.

All subjects will have follow-up visits at 3 months (+/- 7 days), 6 months (+/- 7 days) and 12 months (+/- 14 days) after the onset of treatment to assess efficacy and safety. A strategy will be put in place according to the context of each trial site to assure patients comply with the schedule of scheduled study visits. This will include active tracking of the patients through telephone contact or domiciliary visits.

In addition, a follow-up visit will be performed at 24 months (-1 month/+3 months) to assess the long-term response to treatment and safety. All patients will be invited to present to the 24 months follow-up visit, except those who have been withdrawn from the trial [e.g. for safety reasons (AE leading to treatment discontinuation and rescue treatment received), patients who withdrew consent, and cases of death, or patients who were treatment failure (received rescue treatment at any time during the 12 months follow-up period, including at 12 months visit).

8.2 Baseline Assessments

The following baseline assessments will be done during screening (-28 days to day 0) and after having obtained Informed Consent in order to confirm PKDL diagnosis and verify inclusion and exclusion criteria.

- Demographic data including age and gender
- Medical history including relevant past history, previous VL episode, previous history of PKDL, concomitant medications
- Clinical examination: Physical examination including clinical signs, skin lesions, PKDL assessment, body weight, height, vital signs (Temperature, Heart rate and Blood pressure), spleen and liver size
- Clinical safety laboratory evaluations:
 - Haematology: CBC, including total WBC with differential, platelets
 - Biochemistry: Alanine aminotransferase (ALT), Aspartate aminotransferase (AST), total bilirubin (TBIL), Creatinine (CRE), Potassium
 - Pregnancy test

- HIV test routine counselling for HIV test will be given for patients or patients' parents in case of minors, as part of the study informed consent procedure interview or a separate consent will be requested, according to the local requirements. Testing will be done according to national guidelines and undergo a single rapid diagnostic test for the purposes of the clinical trial. If the RDT for HIV is positive, the patient must be excluded from participating in the clinical trial and receive current standard treatment for PKDL and further assessment and treatment for HIV according to the national HIV treatment Guidelines.
- o rK 39 test
- Skin snip sample for parasitological examination by microscopy and pharmacodynamics assessment (qPCR)
- Blood sample for pharmacodynamics assessment (qPCR)
- $\circ~$ Blood sample for immunological parameters assessment (cytokines IL-2, IFNY, TNFa, IL-10, and Granzyme B)
- Photograph of the patient as per SOP (front and back side with lesions)

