The following eligibility criteria were designed to select subjects for whom the protocol treatment is considered appropriate. All relevant medical and non-medical conditions should be taken into consideration when deciding whether this protocol is suitable for a particular subject. Eligibility criteria may not be waived by the investigator. Any questions regarding a subject's eligibility should be discussed with the DNDi Clinical Manager prior to subject's enrolment.

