4.2 Exclusion criteria

The presence of any of the following will exclude a subject from study enrolment:

- Patients who had prior treatment of PKDL within last 2 years.
- Pregnant and lactating women and women of childbearing age (12 to 55 years) who, before randomization, cannot be assured contraceptive cover during treatment and 5 months thereafter
- Patients with sign and symptoms of severe diseases: defined as suffering from a concomitant severe infection such as TB or any other serious known underlying disease (cardiac, renal, hepatic)
- Severe malnutrition defined by BMI for age WHO reference curves for gender, Z score
 -3 for subjects 6 19 years; BMI < 16 for subjects > 19-years old
- Patients with haemoglobin < 5g/dL
- Patients with abnormal liver function (ALT and AST) tests of more than three times the normal range.
- Patients with total bilirubin levels >1.5 times the upper normal range
- Patients with serum creatinine above the upper normal range
- Patients with serum potassium < 3.5 mmol/L
- Patients with a positive HIV test as applicable
- Patients / guardian not willing to participate
- Patients with history of allergy or hypersensitivity to the relevant study drug
- Patients on immunomodulators

Women who are sexually active and not using an assured method of contraception i.e. either IUCD or medroxyprogesterone acetate (Depo-Provera) but who wish to participate in the trial must sign an additional consent form and agree to receive a long-acting assured form of contraception medroxyprogesterone acetate (Depo-Provera). One injection (which is effective for 3 months) will be administered at baseline, and a 2nd injection will be administered at 3 months visit. This is needed to ensure adequate coverage taking into account the long half-life of approximately 7 days of Miltefosine. Oral contraceptives are not considered adequate

in this context because of the high prevalence of vomiting and diarrhea associated with miltefosine treatment.

Note: Patients not suitable for inclusion in the trial but with confirmed PKDL cases will be treated at the trial sites following National Program treatment policy for PKDL cases.

5 Schedule of events

Protocol activities	Screening	Screening Tre			iod	EOT		Follow-up period			
	D-28 to D0	D1	D8	1 day) D15	D22ª	D30 (+/- 3 days)	3M (+/- 7 days)	6M (+/- 7 days)	12M (+/-14 days)	24M ^f / EOS (-1month/+3 months)	
Consent form	х									х	
Inclusion and Exclusion criteria	х										

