Vital signs and physical exam	х	х	х	Х	х	х	х	х	x	x	
Demographic data and Medical history	х										
Pregnancy test	х										
HIV test	x										
rK 39 test	х										
CBC, ALT / AST, Creatinine, Potassium, bilirubin	x		х	Х	х	x	Xp	x ^b	x ^b		
Skin snip for microscopy and qPCR	x					x	х		X	x	
Blood PD (qPCR)	х					х	х		х		
Tape disc skin sample for qPCR	х					х	х		Х		
Skin biopsy for PK				xc	Xa						
Plasma sample for Miltefosine PK ^a			х	Х	х	х	х				
Plasma sample for Ampho B		х		Х	х	x					
Blood sample for immunological parameters	х			Х		х	х		х		
PKDL evolution assessment, including photographs	х					х	х	х	х	x	
Ambisome monotherapy treatment			Amb injections: D1, D4, D8, D11, D15							1	
Ambisome + miltefosine treatment		Amb injections: D1, D4, D8, D11, D15 + Milt allometric D1-D21									
Safety assessment	SAEs and study related AEs		SAEs and AEs monito							nd AEs related to r procedures	

Protocol Version/Date: V3.0, 25 Feb 2020

a) Assessments to be performed only for the Ambisome® + Miltefosine arm

b) Only if abnormal at the previous assessment in a scheduled or unscheduled visit

c) Day 15 skin biopsy sample only for the Ambisome® monotherapy arm

d) A total of 30 subjects per arm will be included in the Ampho B PK assessment. Day 1 sampling to be performed at the end of infusion and at 2, 4, 8 and 22 hrs after the end of infusion. Day 15 sampling to be performed prior to infusion, at the end of infusion and at 2, 6 and 22 hrs after the end of infusion. One single sample to be collected at D22 for the Ambisome+miltefosine combination arm. One single sample to be collected at D30 for the Ambisome monotherapy arm. f. If the patient has completed 24 months /EOS before the approval of Protocol Amendment V3.0, 25 Feb 2020, the patient can be called as soon as possible for the final visit, this won't be considered a protocol deviation.

6 Enrolment procedures

A computer generated, randomization code will be used for patient treatment allocation to one of the two treatment arms. One set of individuals, opaque, sealed and sequentially numbered envelopes will be provided to the treatment sites, one envelope per patient. Eligible patients who fulfil all the inclusion criteria and have none of the exclusion criteria, and from whom informed consent has been obtained, will be randomized to one of the treatment regimens using the sealed envelopes.

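### The only pregnancy test can be up to 29 days old when teratogenic miltefosine starts, and the first contraceptive injection has no stated day or order relative to that test

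*Protocol*

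**What the plan says.** Section 8.2 lists the pregnancy test among the screening laboratory evaluations and sets one window for all of them: "The following baseline assessments will be done during screening (-28 days to day 0". The schedule of events (section 5) shows a single mark for the test, in the screening column. Section 8.5 names the haematology and biochemistry tests that are repeated during treatment and follow-up; a pregnancy test is not among them.

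Miltefosine in the combination arm runs from the first treatment day: "Milt allometric D1-D21" in the schedule, and "plus miltefosine orally BID administration (allometric dosing) for 3 weeks" in section 7.2. After an interruption of up to 72 hours, "the subject will complete the 21 days of treatment by prolonging the treatment up to Day 24".

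On contraception, section 4.2 excludes women aged 12 to 55 who, before randomisation, "cannot be assured contraceptive cover during treatment and 5 months thereafter". Section 4 adds: "Eligibility criteria may not be waived by the investigator". Section 4.2 then makes provision for one group: "Women who are sexually active and not using an assured method of contraception", meaning an IUCD or medroxyprogesterone. They may enter if they accept the injection: "One injection (which is effective for 3 months) will be administered at baseline, and a 2nd injection will be administered at 3 months visit". Section 8.1 counts the 3-month visit from the onset of treatment, with a tolerance of 7 days either way. Section 8.6.10 explains that pregnant women are excluded because miltefosine is teratogenic, and sets out how a pregnancy is reported and followed.

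**The concern.** The exclusion of pregnant women and the contraception rules exist to prevent exposure in utero. The test is the only scheduled check that a woman is not already pregnant, and it is tied neither to randomisation nor to D1. If it is done early in screening, a conception after it goes unsought until miltefosine has been given.

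The women most exposed to this are those whom section 4.2 admits on no assured method. Their cover begins with an injection on an unspecified day of baseline, possibly well after the test. An injection given after conception does not undo the pregnancy, and reporting and follow-up under section 8.6.10 deal with the consequence rather than prevent it. For a woman already using an IUCD or the injection, the issue is only the age of the test.

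A smaller matter concerns the second injection. It is tied to a visit counted from the start of treatment, not to the date of the first injection, and that visit may be 7 days late.

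**Working it through.** **Test to first dose.** Inputs: test window D-28 to D0 (section 8.2 and schedule); first miltefosine dose D1 (schedule). The calendar includes a D0, so interval = 1 - (test day).

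| Test day | Days to first dose |
|---|---|
| D-28 | 29 |
| D-14 | 15 |
| D-7 | 8 |
| D0 | 1 |

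The permitted range is 1 to 29 days. A test on D0 or D1 before dosing brings it to 0 to 1 day.

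**Test to first injection (women newly starting contraception).** No order is stated. If test and injection share a visit, the interval is 0. If the test is on D-28 and the injection on D0, it is 0 - (-28) = 28 days, with no later test. That is again a maximum.

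**First to second injection.** The protocol gives no conversion of months to days. Assume 3 months = 91 days and 5 months = 152 days, and read baseline as D0.
- 3-month visit: D1 + 91 = D92; with 7 days either way, D85 to D99.
- First injection on D0: cover ends D0 + 91 = D91. Lapse before the second: none at D85, up to 99 - 91 = 8 days at D99.
- First injection on D1: cover ends D92. Lapse: 0 to 99 - 92 = 7 days.
- Sensitivity for a D0 injection: if it is effective for 90 days the lapse is 0 to 9 days; if for 84 days, 1 to 15 days.

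**Does cover last long enough?** Needed to D21 + 152 = D173, or D24 + 152 = D176 if dosing is prolonged. A second injection at D85 to D99 covers to D176 to D190 at 91 days each, which is enough. It is only just enough at the early end: a second injection before 176 - 91 = D85 falls short if dosing ran to D24, and one before 173 - 91 = D82 falls short if dosing ended on D21. With 84 days of effect, a second injection at D85 covers only to D169, which is 4 to 7 days short.

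**The case against.** The strongest reply is that contraception, not the test, is the main barrier, and that it is fixed in time: section 4.2 requires cover to be assured before randomisation, and section 4 forbids waiving it. That stands, and it rules out any claim that women may start miltefosine without contraception having been arranged. It does not answer the point about the test. Assurance of cover during treatment and afterwards says nothing about a conception that came before the cover began.

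A second reply is that 29 days needs a test on the first permitted day, a fully used window, and allocation to the combination arm. This also stands. The protocol gives no typical screening length and no count of women of childbearing age, so a reader should not take 29 days as usual or derive a number of exposures from it.

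A reader might also infer that an injection on the first screening day leaves several weeks uncovered before the 3-month visit, so that section 4.2 contradicts itself and a third injection is needed. The document does not support that. The D-28 window in section 8.2 governs assessments, and an injection is not one. The protocol's usage also lets baseline mean D0: the synopsis places the first skin snip on day 0, where section 8.4.2 calls the same sample baseline. On the D0 reading, section 4.2 is nearly consistent with itself, and what remains is the short lapse from the visit tolerance.

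**Conclusion.** The point holds for the pregnancy test, and more narrowly for the injection. The only test may precede the first miltefosine dose by up to 29 days, and no written rule would detect a conception in between. This rests on plain text and needs no assumption. For sexually active women newly starting contraception, up to 28 of those days may pass between the test and the injection. The requirement that cover be assured before randomisation limits how late the injection can be, but does not close that interval.

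The injection calendar needs only a clarification: state the day of the first injection and stop the +7-day tolerance from opening a lapse of about 0 to 8 days. That figure assumes a 91-day effect and a D0 injection.

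All intervals are permitted maxima, and the number of women affected cannot be estimated from the protocol. The change should be made because the possible harm is irreversible and the remedy is cheap. Eligibility testing and contraceptive timing are matters for the protocol and cannot be left to an analysis plan.

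**What to change.** - Require a negative pregnancy test on D0/D1 for every woman of childbearing age, by moving the screening test or repeating it. Read it before the randomisation envelope is opened and before the first dose. It has to apply to all such women because allocation is unknown until the envelope is opened.
- For women newly starting contraception, give the first injection at that same visit, after the negative test and before the envelope is opened, so that section 4.2's condition is met.
- Give the second injection no later than 3 months after the first, for example by using only the early side of the 3-month visit window. Confirm for each woman that cover reaches 5 months after her actual last miltefosine dose, since the margin is thin if the second injection is early and dosing ran to D24.
- Enter the test and both injections in the schedule of events, and align sections 4.2 and 8.2.

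The cost is at most one inexpensive test per woman, an occasional late screen failure, and some second-injection visits held a few days earlier. A very recent conception may still be missed by a D0/D1 test, so the risk is reduced rather than removed.
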